6.8 ADJUSTMENT OF STARTING DOSE IN SPECIAL POPULATIONS

Renal impairment

Insufficient data are available to provide a dosage recommendation for LEE011 in patients with renal impairment.

Patients with baseline renal impairment are excluded from the study (serum creatinine > 1.5 or creatinine clearance < 50 mL/min). Patients who experience serum creatinine impairment of grade 3 or higher during the treatment period should discontinue treatment and should be followed for safety assessments.

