5.0 SUBJECT ELIGIBILITY

Eligibility waivers are not permitted. Subjects must meet all of the inclusion and exclusion criteria to be registered and enrolled to the study. Study treatment may not begin until a subject is registered (See Section 14.3).

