5.1 INCLUSION CRITERIA

- 5.1.1 Histologically confirmed diagnosis of hepatocellular carcinoma (mixed HCC/cholangiocarcinoma is allowed).
- 5.1.2 **RB positivity as defined by RB expression (score of 0.5 or 1) with concurrent p16in4a loss (score of 0-2);**
- 5.1.3 Patients must have HCC limited to the liver. There must be no definitive

clinical or radiographic evidence of extrahepatic HCC. Portal lymphadenopathy is permitted as lymphadenopathy is commonly associated with cirrhosis unrelated to malignancy;

- 5.1.4 Absence of occlusive main portal vein thrombus, branch venous thrombus is allowed;
- 5.1.5 Patients with locally advanced HCC not eligible for curative therapies;
- 5.1.6 Age \geq 18 years;
- 5.1.7 Child-Pugh Score A or B7;
- 5.1.8 ECOG Performance score of 0-2;
- 5.1.9 Anticipated life expectancy greater than 6 months;
- 5.1.10 Following baseline laboratory values should be met:
 - 5.1.10.1** Total bilirubin \leq 2.0 x ULN or direct bilirubin \leq 1.5 x ULN in patients with well-documented Gilbert's Syndrome;
 - 5.1.10.2** INR \leq 1.7;
 - 5.1.10.3** Hgb \geq 9.0 g/dl;
 - 5.1.10.4** Alkaline Phosphatase, AST, ALT $<$ 5 times ULN;
 - 5.1.10.5** Platelet count \geq 75,000/mm³;
 - 5.1.10.6** Serum creatinine \leq 1.5 mg/dL or creatinine clearance \geq 50 mL/min;
 - 5.1.10.7** Absolute neutrophil \geq 1,500 cells/mm³;
 - 5.1.10.8** Potassium, total calcium (corrected for serum albumin), magnesium, and phosphorus within normal limits for the institution or corrected to within normal limits with supplements;
- 5.1.11 Women of childbearing potential must have a negative pregnancy test;
- 5.1.12 Prior therapy is allowed provided the following are met: at least 4 weeks since prior locoregional therapy including surgical resection, radiotherapy, or

ablation. Provided target lesion has increased in size by 25% or more or the target lesion was not treated with locoregional therapy;

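### Renal eligibility is internally inconsistent: 5.1.10.6 admits a patient if either creatinine or clearance is within its limit, while 6.8 excludes a patient if either is outside it

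*Combined protocol and SAP*

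**What the plan says.** Section 5.1.10 introduces its list of limits with "Following baseline laboratory values should be met". The renal item, 5.1.10.6, reads "Serum creatinine \leq 1.5 mg/dL or creatinine clearance \geq 50 mL/min".

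Section 6.8, on starting dose in special populations, begins by saying that too little is known to recommend a LEE011 dose in renal impairment. It then states that "Patients with baseline renal impairment are excluded from the study" and adds in parentheses what that means: "serum creatinine > 1.5 or creatinine clearance < 50 mL/min". No unit is attached to the creatinine value there, although 5.1.10.6 gives mg/dL.

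The exclusion list in 5.2 has no criterion based on creatinine or clearance. Section 5.0 says "Eligibility waivers are not permitted". Section 7.2.1 says that eligibility is decided by the criteria in Section 5, and Section 14.1 likewise refers to the criteria in Section 5.0.

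**The concern.** The two sections use the same two measurements and the same two cut-offs, and both join them with the same small word. In an inclusion rule, that word lets one acceptable value suffice. In an exclusion rule, it lets one unacceptable value suffice. The two rules are therefore not opposites of each other, and some patients satisfy both.

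What is at stake is who receives LEE011. If sites follow 5.1.10.6, patients whom 6.8 calls renally impaired can be enrolled, including in the phase Ib cohorts that set the dose, where serum creatinine of grade 3 or higher is listed as a dose-limiting toxicity (Table 6.2). If sites follow 6.8, patients who meet every criterion in Section 5 would be turned away. There is also a later effect. Section 6.12.7 lists a creatinine limit of 1.5 mg/dl among the conditions for a repeat chemoembolization. A patient enrolled on clearance alone, with creatinine above 1.5 that does not change, would not meet that limit.

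**Working it through.** The plan gives no figure on this point to reproduce, so the check is one of logic.

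**Inputs.** Let A stand for creatinine at or below 1.5 mg/dL, and B for clearance at or above 50 mL/min. Both cut-offs appear in 5.1.10.6 and in 6.8. The missing unit in 6.8 is taken to be mg/dL.

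**Rules.**
- 5.1.10.6 admits when (A or B).
- 6.8 excludes when (not A or not B), so it admits only when (A and B).

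| Creatinine | Clearance | 5.1.10.6 | 6.8 | Agree? |
|---|---|---|---|---|
| ≤ 1.5 | ≥ 50 | admits | admits | yes |
| ≤ 1.5 | < 50 | admits | excludes | no |
| > 1.5 | ≥ 50 | admits | excludes | no |
| > 1.5 | < 50 | does not admit | excludes | yes |

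The sections conflict in two of the four combinations. The exact opposite of 5.1.10.6 would be creatinine > 1.5 **and** clearance < 50. The exact opposite of 6.8 would be creatinine ≤ 1.5 **and** clearance ≥ 50.

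**Can the discordant groups occur?** The protocol names no clearance formula. Assume Cockcroft-Gault for illustration: clearance = (140 − age) × weight / (72 × creatinine), multiplied by 0.85 for women. The patients below are invented.

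*Creatinine within limit, clearance below 50:*
- Woman, 72 years, 65 kg, creatinine 1.1: (140 − 72) × 65 × 0.85 / (72 × 1.1) = 3757 / 79.2 = 47.4 mL/min.
- Man, 75 years, 75 kg, creatinine 1.4: (140 − 75) × 75 / (72 × 1.4) = 4875 / 100.8 = 48.4 mL/min.

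Both meet 5.1.10.6 and are excluded by 6.8. The result depends on the assumed weight. With age and creatinine held fixed, clearance reaches 50 at 50 × 79.2 / (68 × 0.85) = 68.5 kg for the woman and 50 × 100.8 / 65 = 77.5 kg for the man. Below those weights each is discordant, and above them neither is.

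*Creatinine above limit, clearance at least 50:* for a man with creatinine exactly 1.5, clearance equals 50 when (140 − age) × weight = 50 × 72 × 1.5 = 5400. At 75 kg this gives 140 − age = 72, or age 68. A younger man of that weight with creatinine only slightly above 1.5 would fall in this group.

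These examples show that both groups can arise at ordinary values. They do not show how common they are.

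**The case against.** The best counter-argument is that the protocol says where eligibility is decided. Section 7.2.1 points to Section 5, Section 14.1 does the same, and Section 14.3 registers patients on a signed inclusion/exclusion worksheet. Section 6.8 is a dosing section, its cut-offs are identical, and its sentence looks like a recap of 5.1.10.6 that was negated carelessly. This carries weight: it makes inconsistent enrolment between patients or staff less likely. It does not remove the conflict. If Section 5 governs, the statement in 6.8 that these patients are excluded is untrue, and the trial can treat people for whom the same paragraph says dosing data are lacking. If 6.8 states the intent, 5.1.10.6 is too wide. One of the two must change.

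It can also be said that the safety consequence is limited. The rat data in Sections 1.7.1 and 1.7.3 describe mainly biliary excretion, chemistry including creatinine is repeated at treatment visits (Tables 7.1 and 10.1), and a rise to grade 3 or higher is already covered in Table 6.2 and in 6.8. These points concern disposition in animals and monitoring after entry. They do not say who may enter.

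Three stronger readings are tempting and not supported:
- A reader might infer that the ban on waivers leaves discordant patients impossible to handle. A waiver is for someone who fails a criterion, and these patients meet 5.1.10.6, so under Section 5 none is needed.
- A reader might infer that many patients are affected because older patients with cirrhosis tend to have creatinine values that mask low clearance. The documents say nothing of the kind.
- A reader might infer harm to enrolled patients. The documents show only that the entry rule conflicts with the protocol's own statement about who is excluded.

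**Conclusion.** The inconsistency is real and should be corrected. The two sections disagree for every patient with exactly one of the two values outside its limit, in both directions. Because Section 7.2.1 points to Section 5, the likely practical result is that such patients can be enrolled and given LEE011 despite 6.8.

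The size in patients is unknown: the documents give no distribution of creatinine or clearance, and Table 10.1 lists creatinine but not clearance among the planned chemistry tests. The stated sample size, power and PFS analysis do not depend on this point. The logical conclusion rests only on the wording of the two sections and on reading the creatinine value in 6.8 as mg/dL. Only the worked examples rest on Cockcroft-Gault and on the assumed ages, weights and creatinine values.

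**What to change.** Reconcile 5.1.10.6 and 6.8 so that both state the same rule, using the same logical connective and the same creatinine unit. The simplest form is to state the rule once in Section 5 and have 6.8 refer to it. Whether one acceptable value suffices or both are needed is a clinical decision for the sponsor, and nothing here favours either. Naming the clearance formula would be useful added detail, but the contradiction does not depend on it.

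The cost is a short wording amendment. Depending on the choice, a few more or fewer patients may be eligible. No analysis or sample-size figure needs to change.

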6.5 TREATMENT DURATION

Patients will receive trial treatment until one of the following criteria applies:

- disease progression,
- unacceptable toxicity or toxicity that results in treatment interruption of >4 weeks,
- patient experiences DLT

- patient decides to withdraw from study, starts a new therapy or is lost to follow up
- discontinuation from the study treatment for any other reason.
- PI or study sponsor discretion

Patients who come off therapy will be followed for survival regardless of cause of treatment discontinuation.”

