6.7 LEE011 DOSE MODIFICATION GUIDELINE- PHASE IB CYCLE 2+ AND PHASE II COMPONENTS

Management of severe or intolerable adverse reactions requires temporary dose reduction and/or interruption of LEE011 therapy. Refer to Table 6.3 for guidance. Dose increases once LEE011 has been reduced are not allowed.

Table 6.3 Dose Modification Guidelines

Dose Level	LEE011	
	Dose	Number of capsules & strength
Highest dose (0)	600 mg	3 x 200 mg capsules
First dose reduction (-1)	400 mg	2 x 200 mg capsules
Second dose reduction (-2)	200 mg	1 x 200 mg capsules
Third dose reduction (-3)	Discontinue Treatment of LEE011	

Recommendations for dose reduction, interruption, of discontinuation of LEE011 in the management of adverse reactions are summarized in Table 6-4, Table 6-5, Table 6-6, and Table 6-7. Clinical judgment and discretion of the treating physician should guide the management plan of each patient based on individual benefit and risk assessment.

**Table 6-4 LEE011 Dose Adjustment and Management Recommendations for
HEMATOLOGICAL ADVERSE REACTIONS**

THROMBOCYTOPENIA	
Toxicity/Grade	Dose Adjustment and Management Recommendations
Grade 1 ($\geq 75 \times 10^9/L$)	No dose adjustment required.
Grade 2 ($\geq 50 \times 10^9/L - <75 \times 10^9/L$)	No dose adjustment required.
Grade 3 ($\geq 25 \times 10^9/L - <50 \times 10^9/L$)	Dose interruption until recovery to grade ≤ 2 . Re-initiate LEE011 at the same dose level. If toxicity recurs at grade 3: discontinue LEE011
Grade 4 ($<25 \times 10^9/L$)	Discontinue LEE011.

Toxicity/Grade	Dose Adjustment and Management Recommendations
Absolute neutrophil count (ANC)	
Grade 1 ($\geq 1.5 \times 10^9/L$)	No dose adjustment required.
Grade 2 ($\geq 1.0 - < 1.5 \times 10^9/L$)	No dose adjustment required.
Grade 3 ($\geq 0.5 - < 1.0 \times 10^9/L$)	Dose interruption until recovery to $\geq 1.0 \times 10^9/L$. Re-initiate LEE011 at the same dose level. 
 If toxicity recurs at grade 3: temporary dose interruption until recovery to $\geq 1.0 \times 10^9/L$ and reduce LEE011 dose to the next lower dose level.
Grade 4 ($< 0.5 \times 10^9/L$)	Dose interruption until recovery to $\geq 1.0 \times 10^9/L$. Re-initiate LEE011 at the next lower dose level. 
 If toxicity recurs at grade 4: temporary dose interruption until recovery to $\geq 1.0 \times 10^9/L$ and reduce LEE011 at the next lower dose level.
Febrile Neutropenia	

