2 QTc 481-500 ms	
Interrupt LEE011
 
Perform a repeat ECG one hour after the first QTcF of ≥ 481ms
 
If QTcF < 481 ms, restart LEE011 at the same dose. No dose adjustment for the first occurrence
 
If QTcF remains ≥ 481 ms, restart LEE011 at the same dose level. No dose adjustments required for the first occurrence
 
If QTcF ≥ 481 ms recurs, discontinue LEE011
 
Repeat ECGs 7 days and 14 days after dose resumption (then as clinically indicated) for any patient who has therapy interrupted due to QTcF ≥ 481 ms

3 QTc ≥ 501 ms on at least two separate ECGs	
Interrupt LEE011
 
 • Consider consulting a local cardiologist • Perform a repeat ECG one hour after the first QTcF of ≥ 501 ms • If QTcF remains ≥ 501 ms, repeat ECG as clinically indicated, but at least once a day until the QTcF returns to < 481 ms.

	
 If QTcF returns to < 481 ms, LEE011 should be reduced by 1 dose level. (please refer to the dosing schedule table) 
Repeat ECGs 7 days and 14 days after dose resumption for any patient who has therapy interrupted due to QTcF \geq501 ms
 
 If QTcF of \geq 501 ms recurs, discontinue LEE011

4 QT/QTc \geq 501 or $>$ 60 ms change from baseline
 
And
 
Torsades de pointes or polymorphic ventricular tachycardia, or signs/symptoms of serious arrhythmia
	Discontinue LEE011

Table 6-7 LEE011 Dose Adjustment and Management Recommendations for ALL OTHER ADVERSE REACTIONS

Grade	Dose Adjustment and Management Recommendations
1	No dose adjustment recommended. Initiate appropriate medical therapy and monitor.
2	
Dose interruption until recovery to grade \leq1. Initiate appropriate medical therapy and monitor.
 
Re-initiate LEE011 at the same dose.
 
 If the same toxicity recurs at grade 2, interrupt LEE011 until recovery to grade \leq1. Re-initiate LEE011 at the next lower dose level.

3	
Dose interruption until recovery to grade ≤ 1. Initiate appropriate medical therapy and monitor.
 
Re-initiate LEE011 at the next lower dose level.
 
 • If toxicity recurs at grade 2: temporary dose interruption until recovery to grade ≤ 1 and reduce LEE011 dose the next lower dose level. • If toxicity recurs at grade 3, discontinue LEE011.
4	Discontinue LEE011 and treat with appropriate medical therapy.

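### After a first drug-related grade 3 creatinine event at 400 or 600 mg that recovers within 4 weeks, section 6.8 stops treatment but Table 6-7 restarts LEE011 one level lower

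*Combined protocol and SAP*

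**What the plan says.** Section 6.8, on starting dose in special populations, has a paragraph on renal impairment. It gives its basis as "Insufficient data are available to provide a dosage recommendation for LEE011 in patients with renal impairment", excludes patients with renal impairment at baseline, and then sets an on-treatment rule: "Patients who experience serum creatinine impairment of grade 3 or higher during the treatment period should discontinue treatment". It names no phase, cycle, dose level, attribution or route back onto drug.

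Section 6.7 is headed "LEE011 DOSE MODIFICATION GUIDELINE- PHASE IB CYCLE 2+ AND PHASE II COMPONENTS". It contains a dose ladder (Table 6.3) and four management tables: 6-4 hematologic, 6-5 hepatic, 6-6 QT, and 6-7, titled "LEE011 Dose Adjustment and Management Recommendations for ALL OTHER ADVERSE REACTIONS". The grade 3 row of Table 6-7 calls for interruption until grade 1 or less, followed by "Re-initiate LEE011 at the next lower dose level". Recurrence at grade 3, or any grade 4 event, ends LEE011. The ladder runs 600, 400, 200 mg, and the step below 200 mg is "Discontinue Treatment of LEE011".

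The text before Table 6-4 adds that "Clinical judgment and discretion of the treating physician should guide the management plan of each patient". Section 6.5 ends treatment for "unacceptable toxicity or toxicity that results in treatment interruption of >4 weeks".

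**The concern.** An investigator managing a creatinine rise in phase II would look in section 6.7. No row there names creatinine, so the residual table applies, and for a first grade 3 event it allows a return to drug at a lower dose. Section 6.8 takes the same patient off treatment. There is no cross-reference in either direction and no stated order of precedence, so two investigators could treat the same event differently and each cite the protocol.

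What is at stake is re-exposure of a patient with recent grade 3 creatinine, in a setting where the protocol says it lacks the data to recommend a dose. This is a question of safety and dosing consistency, not of inference.

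**Working it through.** The plan gives no figure to reproduce. The check sets the rules side by side and finds where they differ.

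**1. Does Table 6-7 reach creatinine?** Tables 6-4, 6-5 and 6-6 have no creatinine row, and Table 6-7 makes no exception for it. Section 9.1 lists elevated creatinine among the grade 3 and 4 events suspected to be related to LEE011. A related creatinine event is therefore inside Table 6-7 as written. Section 6.7 speaks of adverse reactions, a term the protocol does not define. If it means drug-related events, an unrelated creatinine rise falls under 6.8 alone. The overlap is certain only for events at least possibly related to LEE011.

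**2. Is discontinuation in 6.8 permanent?** Section 6.7 uses interruption for a temporary hold and discontinuation for stopping. Section 11 does use the latter word for a hold before biopsy, but gives the length (24-48 hours). Section 6.8 gives no length and no restart criterion, so it reads as permanent.

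**3. Which cases differ?** Take a first creatinine event, at least possibly related, in phase Ib cycle 2 or later or in phase II, that recovers to grade 1 or less within 4 weeks:

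| Dose | Grade | Section 6.8 | Tables 6-7 and 6.3 | Result |
|---|---|---|---|---|
| 600 mg | 3 | stop | restart at 400 mg | differ |
| 400 mg | 3 | stop | restart at 200 mg | differ |
| 200 mg | 3 | stop | next step is stop | agree |
| 600 mg | 4 | stop | stop | agree |
| 400 mg | 4 | stop | stop | agree |
| 200 mg | 4 | stop | stop | agree |

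The rules differ in 2 of 3 × 2 = 6 combinations and agree in 6 − 2 = 4.

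**4. Outside that grid.** A recurrent grade 3 event stops LEE011 under Table 6-7. An interruption of more than 4 weeks stops it under 6.5. Both agree with 6.8. In phase Ib cycle 1, grade 3 or higher creatinine at least possibly related to LEE011 is a DLT under Table 6.2, and section 6.6 gives that patient no further drug, which again agrees with 6.8. If the phase II starting dose were 200 mg, phase II would contain no divergent case.

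**5. How often?** The 2 of 6 counts cases; it is not a rate. The common-event tables in section 1.7.4 (600 mg, n=67) do not list creatinine, and section 9.1 lists it without a frequency.

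**The case against.** The best defence is that an ordinary reading settles the matter. Section 6.8 comes directly after Table 6-7 and names the toxicity, the grade, the period and the action. An event with its own rule on the next page is arguably not an other reaction at all. The tables are described as recommendations guided by clinical judgment, so an investigator who stops for grade 3 creatinine breaches nothing. On this view only a cross-reference is missing.

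Much of that stands. It is a good reason to let 6.8 govern and to rate the point as minor. It does not remove the conflict. Within section 6.7, other most naturally means not covered by Tables 6-4 to 6-6. The 6.8 heading concerns starting dose, so a reader handling an on-treatment event may never reach it. The judgment clause does not say which rule prevails, and could be cited for the very restart that 6.8 rules out. Where the authors wanted no rechallenge for hepatic events, they wrote that into the table.

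A reader might also infer that the cycle 1 DLT rule proves Table 6-7 wrong. The documents do not support that. Table 6.2 makes most other grade 3 non-hematologic events cycle 1 DLTs as well, and Table 6-7 allows restart after those in later cycles. A stricter rule in cycle 1 is a general feature of the plan and says nothing particular about creatinine.

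**Conclusion.** Wrong as written, but minor. In phase Ib from cycle 2, or in phase II, sections 6.7 and 6.8 give opposite instructions for a first grade 3 creatinine event, at least possibly related to LEE011, at 400 or 600 mg, that recovers to grade 1 or less within 4 weeks. Section 6.8 should govern. Outside the phase Ib cycle 1 DLT criteria it is the only LEE011 dosing rule that names creatinine; section 6.12.7 names it too, but only as a condition for repeat chemoembolization. It also covers the whole treatment period and rests on a stated lack of dosing data.

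The conclusion assumes that discontinuation in 6.8 is permanent and that Table 6-7 covers whatever Tables 6-4 to 6-6 leave out.

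A reader might infer that every creatinine event of grade 3 or higher is handled inconsistently, or that many patients are exposed. Neither follows: both rules stop the drug at 200 mg, at grade 4, on grade 3 recurrence and after more than 4 weeks off drug, and the documents give no event rate. Nor does the point reach the trial's statistical conclusions. The MTD rests on cycle 1 only, where Table 6-7 does not apply, and the sample size and the primary PFS analysis do not depend on which creatinine rule is followed.

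**What to change.** Add an exception to Table 6-7: for serum creatinine of grade 3 or higher, regardless of attribution, permanently discontinue LEE011 and follow for safety per section 6.8; further chemoembolization remains subject to the creatinine limit in section 6.12.7 (1.5 mg/dl). Add a sentence to section 6.8 saying that its rule overrides Table 6-7.

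The wording on chemoembolization is needed because 6.8 speaks of discontinuing treatment, while section 6.2 defines study treatment as LEE011 plus chemoembolization. The line above takes 6.8 to mean LEE011. If the sponsor means both components, the exception should say so.

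The cost is two short text changes in one amendment, with no added procedures. The downside is that a few patients with reversible grade 3 creatinine lose the option of rechallenge at a lower dose. If the sponsor prefers to keep that option, it should amend 6.8 instead. Either way, only one rule should remain.

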6.9 CONCOMITANT MEDICATIONS

Permitted Concomitant Therapy

Medications required to treat AEs, manage cancer symptoms, concurrent diseases and supportive care agents, such as pain medications, anti-emetics and anti-diarrheal are allowed.

The patient must be told to notify the investigational site about any new medications s/he takes after the start of the study treatment. All medications (other than study drugs) and significant non-drug therapies (including vitamins, physical therapy and blood transfusions) administered within 30 days of study entry and during the study must be listed on the Concomitant medications/Significant non-drug therapies section of the patient record.

Bisphosphonates and Denosumab

Bisphosphonates and denosumab are permitted for the treatment of osteoporosis and prevention of skeletal related events for patients with bone metastases. Chronic concomitant bisphosphonate/denosumab therapy for the prevention of bone metastasis is not permitted.

Hematopoietic Growth Factors

Hematopoietic growth factors may be used according to ASCO guidelines.

Palliative Radiotherapy

Palliative radiation is permitted if done solely for bone pain relief. It should not be delivered to a target lesion and it should not encompass more than 25% of irradiated bone marrow. Refer to the LEE011 (LEE011) Investigator's Brochure, Appendix table 1, and Appendix table 2 for information on possible interactions with other drugs.

Permitted Concomitant Therapy Requiring Caution

Medications to be used with caution during LEE011 in this study are listed below (**see Table 2**). This list is not comprehensive and is only meant to be used as a guide. Concurrent use of CYP1A2 substrates is not expected to lead to clinically important drug-drug interactions, therefore their use is not regulated. These medications should be excluded from patient use if possible. If they must be given, then use with caution and consider a LEE011 interruption if the concomitant medication is only needed for a short time (**See Appendix Table 1**):

- Moderate inhibitors or inducers of CYP3A4/5;
- Sensitive substrates of CYP3A4/5 that do not have narrow therapeutic index;
- Strong inhibitors of BSEP;
- Sensitive substrates of the renal transporters, MATE1 and OCT2;
- Sensitive substrates of BCRP;
- Medications that carry a possible risk for QT prolongation

Prohibited Concomitant Therapy

The following medications are prohibited during study treatment in the study (**see Appendix Table 2**). This list is not comprehensive and is only meant to be used as a guide:

- Strong inhibitors or inducers of CYP3A4/5;
- Substrates of CYP3A4/5 with a narrow therapeutic index;
- Medications that carry a known risk for QT prolongation;
- Herbal medications/preparations, herbal dietary supplements;
- Other investigational and antineoplastic therapies not part of the study;
- Herbal medications include, but are not limited to: St. John's Wort, Kava, ephedra (ma huang), ginkgo biloba, dehydroepiandrosterone (DHEA), yohimbe, saw palmetto, black cohosh and ginseng. Patients should stop using all herbal medications and dietary supplements at least 7 days prior to first dose of study treatment.

